Definition of cognitive deficit: Because we are proposing a cognitive test battery that results in many scores per patient, it is essential to assess the results with an analytic approach that makes use of all the information without redundancy. We plan to define cognitive deficit from our raw test scores by using a factor analysis. Factor analysis is a technique that has the objective of representing the large, overlapping set of raw test scores by a smaller set of factors through transformation based on the intercorrelations among the test scores. Each "factor" represents a hypothetical, unobservable characteristic that can be interpreted as a discrete domain of

cognitive functioning. The first factor is based on the computation of principal components and is the linear combination of the items, subject to a normalizing constraint, which accounts for the greatest amount of variance across patients. The second factor is that linear combination, uncorrelated with the first, which accounts for the next largest amount of variance, and so on. An orthogonal rotation will be done for interpretability of the results. The factor analysis can thus identify the independent (orthogonal) domains of cognitive function, as measured by the full battery of cognitive tests, and reduces the number of outcomes to be analyzed. Factor analysis makes use of all the information provided by the patient to return independent, continuous and standardized summary measures for assessment. By measuring each domain with several tests, and combining the scores using the factor analytic solution, we will also enhance the reliability of the overall measurement of each domain. Based on our extensive experience with the test battery, we expect to obtain factor scores for four separate domains of cognitive function.

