Hydroxychloroquine and Cognitive Function after Surgery

NCT03025087

[figure not shown]
Document Date: 11/29/2020

Hydroxychloroquine and Cognitive Function after Surgery

Purpose of the study

As our population ages, the manifestations of systemic atherosclerosis (stroke, cognitive impairment) extend the burden on the healthcare delivery system. The consequences of atherosclerosis are particularly relevant during surgery, where perioperative neurologic events can have a dramatically detrimental effect on the duration and quality of survival. The long-term objective of our multidisciplinary Neurological Outcome Research Group (NORG) is to understand the mechanisms underlying neurologic and neurocognitive dysfunction after surgery and to reduce the incidence of these devastating outcomes.

This study is a pilot investigation intended to gather preliminary information to assess the efficacy of hydroxychloroquine to preserve blood brain barrier integrity, decrease inflammation, and improve cognitive function after surgery including cardiac surgery with cardiopulmonary bypass (CPB). Our study is based on a model (see Figure) that surgical trauma (irrespective of type of surgery) with general anesthesia evokes a systemic inflammatory response.(1) Damage-associated molecular pattern (DAMPs), including HMGB1, are released in the systemic circulation contributing to the permeability of the blood–brain barrier (BBB). Opening of the BBB allows peripheral cytokines and alarmins to enter the brain and the CNS, causing neuroinflammation. In the hippocampus, HMGB1 activates receptor for advanced glycation end products (RAGE) signaling thus perpetuating the inflammatory response and further contributing to neuroinflammation, including de novo synthesis of cytokines like TNF- α and IL-1 β . Activation of this positive feedback loop accounts for memory dysfunction and possibly localized synaptic/neuronal deficits.

Preliminary data from our pilot study (Pro00045387) indicates that blood brain barrier disruption occurs in about 60% of cardiac surgery patients and 50% of noncardiac surgery patients. Including an expanded cohort of patients will allow the investigation of differences in the outcomes of interest by surgery type.

The primary purposes of this pilot investigation are to:

1. Obtain data on the pharmacokinetics of hydroxychloroquine during surgery.
2. Determine the effect of hydroxychloroquine upon blood brain barrier (BBB) integrity after surgery.

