Patients selected for enrollment will be informed of the study, as well as the risks and benefits of participation. Patients will be invited to participate and a log of all patients and those that accept and reject the invitation will be kept. As part of enrollment, a Mini Mental Status Exam (MMSE) will be performed and all patients scoring < 26 will be excluded to minimize the possibility of early dementia in our patient samples. Similarly patients scoring ≥ 27 on the Center for Epidemiological Studies – Depression (CES-D) scale (indicating severe depression) will be excluded. If patients develop renal failure (GFR < 30 ml/min/1.73 sq.m) postoperatively (after consent), they will not receive gadolinium based contrast for MRI.

Hydroxychloroquine Administration

The average adult dose of HCQ in the initial management of lupus is 400 mg once or twice daily. Similarly, the initial dose in rheumatoid arthritis is 400-600 mg daily.(31) Recently, HCQ has been administered safely to 19 subjects at a dose of 1000 mg daily as an adjuvant to lung cancer chemotherapy (median follow-up 9.1 months).(32) We therefore propose a dose escalation protocol as follows:

- Phase 1 – 6 evaluable subjects (3 cardiac, 3 noncardiac): 1000 mg HCQ on the day prior to surgery.
- Phase 2 – 6 evaluable subjects (3 cardiac, 3 noncardiac): 1000 mg HCQ on the day prior to surgery followed by 400 mg daily until the day of MRI imaging on postoperative day 1-5.
- Phase 3 – 6 evaluable subjects (3 cardiac, 3 noncardiac): 1000 mg HCQ on the day prior to surgery followed by 400 mg twice daily (800 mg total) until the day of MRI imaging on postoperative day 1-5.
- Phase 4 – 6 evaluable subjects (3 cardiac, 3 noncardiac): 1000 mg HCQ on the day prior to surgery followed by 500 mg twice daily (1000 mg total) until the day of MRI imaging on postoperative day 1-5.
- Phase 5 – 6 evaluable subjects (3 cardiac, 3 noncardiac): 1000 mg HCQ 1-2 hours after separation from CPB or at end of noncardiac surgery followed by the highest tolerated dose from the previous 4 phases divided into 2 equal daily doses until the day of MRI imaging on postoperative day 1-5.

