Neurologic history and physical exam will be completed preoperatively (baseline), six weeks (\pm 2 weeks), and one-year (\pm 1 month) after surgery. To allow comparison with stroke trials, the NIH Stroke Scale (NIHSS) will be used. NIHSS, a serial measure of neurologic deficit, is a 42-point scale that quantifies neurologic deficits in 11 categories, and is a sensitive and reliable measure to detect a change in neurologic function. To ensure consistency and to enhance the detection of subtle neurologic changes, each patient will have repeated examinations by the same examiner when possible.

Neuroimaging Procedures

Imaging will be performed on a 3T scanner (Siemens Healthcare, Erlangen Germany) in the Center for Advanced Magnetic Resonance Development in the Department of Radiology.

Patients are expected to undergo postoperative MR imaging once hemodynamically stable, typically around 1-5 days after surgery. Imaging protocol will include standard product pulse sequences, including high resolution structural T1-weighted images co-localized with contiguous multidirection diffusion-weighted imaging with b value of 1000. In addition, contiguous T2-FLAIR images will be obtained prior to and following administration of a standard dose of gadolinium contrast agent (e.g. 0.3 ml/kg gadobutrol or 0.1 mmol/kg gadopentetate dimeglumine). Gadavist (generic name gadobutrol) or MultiHance (generic name gadobenate dimeglumine) will be injected as a rapid intravenous bolus during which a time series of 8 T1 maps acquired with a fast T1-mapping sequence with partial inversion recovery will be performed, following a single pre-contrast T1 map. Total imaging time is approximately 45 minutes. Patients who develop a GFR <30 after surgery will not receive gadolinium but will continue to be followed for adverse events until they are discharged from the hospital, at Week 6 and 1 Year study follow up.

If an orbital radiograph is requested for MRI clearance, it will be completed prior to the scheduled MRI and will be done here at Duke facility. The orbital x-ray will be completed if the subject has no medical records acceptable for clearance.

MR Image review for presence of BBB disruption

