A board-certified neuroradiologist, blinded to the clinical and surgical variables, will read the MRI, and also review the precontrast and postcontrast FLAIR images for the presence of HARM (hyperintense acute reperfusion marker) and classify it by location (sulcal, ventricular, and/or generalized) and severity (mild, moderate, or severe), according to the classification scheme described by Merino et al.(9)

Quantitative DCE MRI of BBB disruption

Using T1 time series data, we will calculate the rate at which the contrast agent passes from the vascular compartment into the tissue compartment, K_i , using the Patlak formulation of tracer leakage.(33) Plasma levels of gadolinium will be sampled from a region-of-interest in the sagittal sinus. Parenchymal region-of-interest measurements will be made in the white matter.

Quality of Life Assessment

Quality of life will be measured in conjunction with each cognitive assessment at baseline, 6-weeks (\pm 2 weeks),, and 1-year (\pm 1 month) in all enrolled patients. We will use an instrument that includes a measure of functional status derived for use in cardiovascular populations (the Duke Activity Status Index or DASI), psychological measures including depression (the CES-D), the State Trait Anxiety Inventory (STAI), the Hopkins Symptom Checklist (SCL-90), social/role functioning (including employment status), and the Short Form 36 question (SF 36) generic quality of life instrument.

Blood Sampling

Blood samples will be drawn for analysis as a part of this study. One 10 ml sample of peripheral blood will be obtained from each patient prior to surgery and stored. Genomic DNA for analysis will be obtained from this sample and analyzed for the presence of candidate SNPs (single nucleotide polymorphisms) including APOE. 10 ml of blood will also be sampled at baseline, end of CPB, postoperative days 1, 2 and day of the MRI scan, and at 6 weeks (\pm 2 weeks), and 1 year (\pm 1 month) follow-up for assessment of inflammatory and proteomic markers. In addition, 10ml of blood will be drawn to assess HCQ drug levels at end of CPB and day of the MRI scan. Subjects will have the option to sign the Genomic and Proteomic Database Repository (IRB#00015651) consent form, allowing the banking of any remaining plasma and DNA samples for future research. If a creatinine level is not drawn for standard of care post-operatively, one 6ml blood sample will be drawn to assess kidney function (GFR \geq 30 ml/min/1.73 sq.m) for

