gadolinium administration safety. Up to 106 ml of blood will be collected during the 12 month study participation period.

Ophthalmic Assessments

Hydroxychloroquine associated retinopathy is rare and thought to be associated with cumulative dosage and with chronic administration. Although toxicity is not expected in the short-term dosing schedule in this protocol, ophthalmic assessment will be performed on every subject consented as an additional measure of safety. Ophthalmic assessments will occur at baseline and at 6 weeks after surgery. Each assessment will take approximately 1.5 hrs and will include visual acuity, optical coherence tomography (OCT) of the macula, and multi-focal electroretinogram (ERG). Ophthalmic assessments will be performed in the undilated eye, but the eye may need to be dilated in the event of minuscule pupils. A report confirming the absence of retinal abnormalities (that are contraindications to hydroxychloroquine administration – see exclusion criteria #18) will be provided to the study team by an ophthalmologist ([name]) prior to initial dosing. The 6-week report will document serial changes and will be evaluated as part of the safety profile.

ECG for QTc evaluation

Standard of care (SOC) ECG will be used to evaluate QTc prior to HCQ dosing. For males QTc>450msec and for females>470msec will be ineligible to receiving HCQ dosing that day. If no ECG will be obtained per SOC, the research team will perform an ECG at baseline and prior to daily HCQ dosing.

Standard of Care

- Anesthesia (premedication, choice of anesthetic technique and drugs to be administered) per standard of care
- Surgical and postoperative care per standard of care
- Clinical status will be monitored throughout the duration of the procedure
- Standard of Care ECG if performed will be used for evaluation of QTc prior to HCQ dosing throughout the study.

Selection of Subjects

To be eligible for inclusion into the study, each patient will have to fulfill the following criteria:

Inclusion Criteria

1. Male or female, age \geq 50 years old.
2. Patients scheduled to undergo cardiac surgery (CABG, CABG + Valve, Valve) with CPB or general surgery (e.g. orthopedic, abdominal, urological).
3. Patient has voluntarily signed and dated the study-specific informed consent form approved by Duke University Health System Institutional Review Board (DUHS IRB)

Exclusion Criteria

1. Cardiac surgery scheduled to be performed without cardiopulmonary bypass

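### Phase 5 assures only one post-dose HCQ level per subject: the first tube is pre-dose in the 3 cardiac subjects and has no defined time in the 3 noncardiac subjects (minor)

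*Combined protocol and SAP*

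**What the plan says.** All references are to the combined protocol and SAP.

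- **Purpose of the study.** The first of four primary purposes is "Obtain data on the pharmacokinetics of hydroxychloroquine during surgery" and the second is "Determine the effect of hydroxychloroquine upon blood brain barrier (BBB) integrity after surgery". The third and fourth concern inflammation, and the links between HCQ, inflammation, barrier disruption and neurological or cognitive function.
- **Hydroxychloroquine Administration.** There are five phases, each with 3 cardiac and 3 noncardiac evaluable subjects. Phases 1-4 all begin with 1000 mg the day before surgery. Phase 5 has no preoperative dose. It begins with "1000 mg HCQ 1-2 hours after separation from CPB or at end of noncardiac surgery" and continues twice daily up to the scan.
- **Blood Sampling, drug levels.** "10ml of blood will be drawn to assess HCQ drug levels at end of CPB and day of the MRI scan". No other HCQ sampling time is given for Phase 5 or for noncardiac subjects.
- **Blood Sampling, markers.** "10 ml of blood will also be sampled at baseline, end of CPB, postoperative days 1, 2 and day of the MRI scan", and again at 6 weeks and 1 year. These tubes are for inflammatory and proteomic markers.
- **Blood Sampling, volume.** "Up to 106 ml of blood will be collected during the 12 month study participation period".
- **Inclusion Criteria, item 2.** Cardiac patients operated on with CPB and general surgery patients are both eligible.
- **Neuroimaging Procedures.** "Patients are expected to undergo postoperative MR imaging once hemodynamically stable, typically around 1-5 days after surgery".

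**The concern.** The HCQ sampling times suit a drug given before surgery. In Phases 1-4 a level at the end of bypass shows what was on board during the operation. Phase 5 reverses the order of dose and tube, but the sampling times were not changed to match.

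Phase 5 is the only phase that starts treatment after surgery. Purposes 2 to 4 all concern what HCQ does after the operation, so some description of exposure after a postoperative start is useful. The documents give no absorption data, so measured levels are the trial's only information on that exposure. One of the two planned levels is used, in the cardiac subjects, on blood that contains no study drug by design. In the noncardiac subjects it is tied to an event that does not occur.

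**Working it through.** **Step 1. How many HCQ tubes per subject?** The stated blood ceiling can be rebuilt from Blood Sampling, with k the number of HCQ tubes:

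volume = 10 (DNA) + 7 × 10 (markers: baseline, end of CPB, days 1 and 2, MRI day, 6 weeks, 1 year) + k × 10 (HCQ) + 6 (creatinine)

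- k = 1: 10 + 70 + 10 + 6 = 96 ml
- k = 2: 10 + 70 + 20 + 6 = 106 ml, the stated figure
- k = 3: 10 + 70 + 30 + 6 = 116 ml

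So the plan budgets at most two HCQ tubes per subject.

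**Step 2. Where does the first Phase 5 tube fall?**

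- Cardiac (3): the tube is at end of CPB and the dose is 1-2 hours after separation, so the tube precedes the dose by about 1-2 hours.
- Noncardiac (3): there is no CPB, so the time is undefined. Read as end of surgery, it coincides with an oral or nasogastric dose.

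The second tube, on MRI day, follows the first dose in all 6. Evaluable subjects are by definition those who complete the MRI, so this level is the assured one: 6 × 1 = 6.

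**Step 3. Whole-trial count.** Evaluable subjects: Phases 1-4 have 12 cardiac and 12 noncardiac; Phase 5 has 3 and 3; total 30.

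| Group | Post-dose levels if the noncardiac first tube is at end of surgery | Post-dose levels if noncardiac subjects have no first tube |
|---|---|---|
| Phases 1-4 cardiac (12) | 12 × 2 = 24 | 12 × 2 = 24 |
| Phases 1-4 noncardiac (12) | 12 × 2 = 24 | 12 × 1 = 12 |
| Phase 5 cardiac (3) | 3 × 1 = 3 | 3 × 1 = 3 |
| Phase 5 noncardiac (3) | 3 × 1 = 3 | 3 × 1 = 3 |
| Post-dose total | 54 | 42 |
| Planned tubes | 30 × 2 = 60 | 15 × 2 + 15 × 1 = 45 |
| Share post-dose | 54/60 = 90% | 42/45 = 93% |
| Subjects with one post-dose level | 6 of 30 (20%), all Phase 5 | 15 + 3 = 18 of 30 (60%) |

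Within Phase 5, 6 of 12 planned tubes are post-dose under the first reading and 6 of 9 under the second.

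**Step 4. After the change.** With every first tube placed after a dose, 30 × 2 = 60 of 60 planned levels are post-dose.

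**The case against.** The strongest reply is that nothing in the plan depends on the missing level. Purpose 1 concerns pharmacokinetics during surgery, and Phase 5 has no drug on board then by design. The safety review before escalation looks at adverse events, QTc, hemodynamics and laboratory values, not drug levels. The regression in Neurocognitive Analyses has no HCQ concentration term. The tube taken on the day the barrier is imaged is kept, and the study is a pilot. All of this stands, and it is why the point is minor.

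It can also be said that end of surgery is the natural reading for noncardiac subjects, because the Phase 5 dosing line itself pairs bypass separation with the end of noncardiac surgery. That is fair, and it removes any shortfall in Phases 1-4. It does not help Phase 5, where that time is also the dosing time.

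Marker blood is already drawn on days 1 and 2 and might be assayed for HCQ. That is possible, but the plan neither schedules it nor says whether sample type and volume would allow it.

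Several stronger readings are tempting, and the documents do not support them:

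- *Half the Phase 5 tubes contain no drug.* This is shown only for the 3 cardiac subjects. An untimed noncardiac tube could be drawn after the dose.
- *Only 42 of 60 levels are post-dose.* This mixes two readings. If noncardiac subjects have no first tube, the denominator is 45. If they have one around surgery, those in Phases 1-4 were dosed the day before, and the count is at least 54 of 60.
- *The scan day, which varies with recovery, is a Phase 5 flaw.* It is common to all phases.
- *An early Phase 5 level could be set beside the end-of-CPB level of Phases 1-4.* Those levels follow a dose given the day before, so time since dose would not match.

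**Conclusion.** The concern holds in a limited form, and its severity is minor. In Phase 5, 6 of 30 evaluable subjects (20%), each subject has one assured post-dose HCQ level. The first tube is pre-dose in the 3 cardiac subjects and undefined, or at the moment of dosing, in the 3 noncardiac subjects. The noncardiac wording gap also touches the 12 noncardiac subjects of Phases 1-4. There it bears on purpose 1, but only if they would otherwise have no first tube.

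This rests on three assumptions: that end of CPB and separation from CPB are essentially the same moment, that the first dose is given as scheduled, and that sites follow the written times.

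The loss is descriptive. A reader might infer that the gap leaves a null Phase 5 result uninterpretable, or that purpose 1 fails there. Neither follows: one more level in 6 subjects would not separate low exposure from lack of effect, and purpose 1 is not at stake in Phase 5. No sample size, safety rule or endpoint changes. The tube is still worth moving, because a sample known in advance to hold no study drug adds almost nothing.

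**What to change.** 1. In Phase 5, move the first HCQ tube to a fixed time after the first dose, the same for cardiac and noncardiac subjects. The sponsor should set that time from absorption data, since the documents give none. If a separate draw is impractical, take the tube with the postoperative day 1 marker draw.
2. Keep the MRI-day HCQ tube, and leave the marker tubes at their present times.
3. In Phases 1-4, define the first HCQ tube of noncardiac subjects as end of surgery.
4. Record actual dose and draw times, and report each level against time since first dose.

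The cost is a change to the sampling wording, one re-timed draw in 6 subjects, and loss of a pre-dose blank. No subjects are added and the ceiling stays at 106 ml, because a budgeted tube is moved rather than added. On the day 1 option, the tube repeats the MRI-day tube in any subject scanned on day 1. The return is a second post-dose level after a postoperative start. The change does not give a time-matched comparison with Phases 1-4 and does not remove the variable scan day.

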In animal models, the aminoquinolines have been shown to be protective against BBB dysfunction. In one study, mice were pretreated with either chloroquine or saline for six consecutive days and then given a dose of kainic acid, which is known to induce seizures and cause BBB dysfunction.(30) Animals treated with chloroquine had less IgG and serum protein extravasation into the brain compared with controls, indicating better preservation of the BBB.

In a recently completed study at Duke (unpublished data), adult male Sprague-Dawley rats underwent 60 minutes of deep hypothermic circulatory arrest (DHCA) at 18°C after being pretreated with either Chloroquine (25mg/kg) vs. PBS vehicle, or a selective quinone reductase 2 (QR2) inhibitor (25mg/kg) vs. 50% DMSO vehicle administered intraperitoneally 2 hours before CPB (n=3-4). Brain magnetic resonance imaging (MRI) was performed on postoperative day (POD) 1 using a 7T Bruker Biospec horizontal bore scanner, and neurologic function scores were assessed on POD 1 and 2. Brain samples harvested 48 hours after CPB/DHCA were used to quantify necrotic neurons (acid fuchsin-celesteine blue) in 5 representative areas of cortex and CA1 hippocampus. MRI analysis revealed a decrease in blood brain barrier permeability as measured by gadolinium chelate in animals treated with chloroquine or selective QR2 inhibitor compared to their respective control groups ($p < 0.05$). Histologically, animals treated with chloroquine or QR2 inhibitor exhibited lower numbers of cortical and hippocampal necrotic cells compared to vehicle-treated animals ($p < 0.05$, respectively). QR2 inhibition also improved neurologic function on POD1 (neurologic score 2.33 ± 0.58 in QR2 inhibitor vs 4.33 ± 0.58 in DMSO vehicle; $p < 0.05$).

As a consequence of its anti-inflammatory, antimicrobial, and BBB preservation properties and its long history of safety, particularly with short-term use, HCQ may be an ideal candidate for evaluation as a neuroprotective agent following surgery.

Design & Procedures

This study is a pilot investigation intended to gather preliminary information to assess the efficacy of hydroxychloroquine to preserve blood brain barrier integrity and improve cognitive function after surgery. In this clinical trial, up to 50 informed and consenting patients ≥ 50 years of age will be prospectively enrolled over a 1-year period to provide 30 evaluable subjects.

Study Procedure

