All doses will be provided per oral or per nasogastric tube that is routinely placed after cardiac surgery. A total of 50 patients are proposed to account for drop-outs (drug intolerance, MRI exclusions; unwilling to return at 6 weeks). Subject who do not complete MRI during their hospitalization will continue to be followed at 6 weeks and 1 year, however, they will not be included as an evaluable subject and will need to be replaced to meet the required number of evaluable subject per phase.

A safety review will be done prior to dose escalation. After all subjects in each dose group have completed study procedures through post-operative Day 4-5, all available safety information will be reviewed by the principal investigator (PI) and [name] (Anesthesiology CRU Director). If there are no clinically significant safety concerns at a given dose, the study may continue escalation to the next higher dose.

Safety will be assessed by the following outcome measures:

- Examination of adverse events
- Examination of QTc values
- Examination of abnormal changes in hemodynamic measurements (heart rate, blood pressure)
- Clinically significant abnormal changes in laboratory values compared with baseline (hematology, chemistry, urinalysis)
- Evaluation of concomitant medications and CPB procedure parameters (time on CPB, cross-clamp time, urine output during surgery, any difficulty separating from CPB [such as the need for intra-aortic balloon pump, left ventricular assist device or re-institution of CPB]) will also be taken into consideration in the evaluation of subject safety.

Neuropsychological Assessment Procedures

Once identified as meeting study criteria and consented for participation, patients will be tested prior to surgery, at 6 weeks (\pm 2 weeks) and 1 year (\pm 1 month) post-surgery with the cognitive battery detailed below. All testing will be conducted by experienced psychometrists either in the patient's hospital room or in the Behavioral Testing Laboratory located in Duke South.

1. *Hopkins Verbal Learning Test - Revised (HVLT-R)* - The Hopkins Verbal Learning Test is a word-list learning task used to assess memory. Over three trials, a 12-word list of three semantic categories is presented to the examinee who then recalls as many words as possible, in any order. After a 20-30 minute, a delayed recall and a delayed recognition trial are administered.

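### Does defining evaluability by inpatient MRI alone undermine the 6-week cognitive primary endpoint?

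*Combined protocol and SAP*

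**What the plan says.** Design & Procedures states that up to 50 patients "will be prospectively enrolled over a 1-year period to provide 30 evaluable subjects". Hydroxychloroquine Administration divides these into five phases of 6, each with 3 cardiac and 3 noncardiac subjects. It explains the larger number thus: "A total of 50 patients are proposed to account for drop-outs (drug intolerance, MRI exclusions; unwilling to return at 6 weeks". The next sentence keeps subjects without an inpatient MRI in follow-up at 6 weeks and 1 year, but "they will not be included as an evaluable subject and will need to be replaced".

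Cognitive testing does not depend on MRI. Neuropsychological Assessment Procedures says: "Once identified as meeting study criteria and consented for participation, patients will be tested prior to surgery, at 6 weeks", and then again at 1 year. Neurocognitive Analyses defines the primary endpoint as the 6-week minus baseline change in the continuous cognitive score. It then specifies a regression of that change on BBB disruption, adjusted for age, education, baseline score and surgery type.

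On imaging, Neuroimaging Procedures says: "Patients are expected to undergo postoperative MR imaging once hemodynamically stable". The scan includes FLAIR before and after gadolinium, and T1 maps during the contrast bolus. For postoperative GFR below 30, Study Procedure says "they will not receive gadolinium based contrast for MRI", and Neuroimaging Procedures says: "Patients who develop a GFR <30 after surgery will not receive gadolinium but will continue to be followed for adverse events".

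**The concern.** Three things look wrong.

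- **Mismatch with the primary endpoint.** A subject with an MRI but no 6-week test counts as evaluable. A subject with a 6-week test but no MRI has the primary endpoint and is labelled not evaluable. MRI comes after dosing and depends on haemodynamic stability. If the label were carried into the cognitive analysis, that analysis would be conditioned on a post-treatment event and would drop data already collected.
- **Contrast.** The rule speaks of completing MRI and does not mention gadolinium. Both BBB readings, the FLAIR reperfusion marker and the transfer rate Ki, need contrast. Read literally, a scan that gives neither reading could fill one of the three places in a phase-by-surgery cell.
- **Replacement.** The 50 allows for patients who will not return at 6 weeks, yet replacement is required explicitly only for a missing MRI.

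A reader therefore cannot tell from the words alone whether the 30 means 30 with a BBB reading, 30 with a 6-week score, or 30 with both.

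**Working it through.** **The plan's own figures.** 5 phases × 6 = 30, which matches the stated number. The 50 cannot be derived, because no drop-out rate is given. Working back, 1 − 30/50 = 0.40, so the cap tolerates a total loss of 40%. No power calculation rests on the 30, so none can be wrong on this account.

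**Where the term is used.** Evaluable appears in Design & Procedures and in Hydroxychloroquine Administration, each time as an enrolment or phase count. Neurocognitive Analyses does not use it. Subjects without MRI keep their 6-week visit, so their scores exist. Analysing the 6-week change in everyone dosed who has both scores already agrees with the text.

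**What an MRI-based count serves.** One stated primary purpose is: "Determine the effect of hydroxychloroquine upon blood brain barrier (BBB) integrity after surgery". MRI also fixes other data. One of the two drug-level samples and one inflammatory-marker sample are taken on the scan day (Blood Sampling), and dosing in Phases 2–5 runs to the scan day. MRI falls on postoperative days 1–5, and the safety review before escalation follows Day 4–5 procedures. A count that waited for the 6-week score could not close a phase at that time.

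**What depends on the unwritten analysis set.** All rates here are assumptions: MRI non-completion m = 20–30%, and 6-week loss d = 10–20%, equal with and without MRI.

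| Quantity | Formula | Result |
|---|---|---|
| Dosed to obtain 30 MRI completers | 30/(1−m) | 37.5 (38) to 42.9 (43) |
| Of those, with a 6-week score | 30(1−d)/(1−m) | 33.8 at 20%/10%; 34.3 at 30%/20%; 30.0 and 38.6 for the other two pairings |
| MRI completers with a 6-week score | 30(1−d) | 27 to 24 |

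The gap between the last two rows is what would be lost if analysts restricted the cognitive analysis to MRI completers. Nothing in the plan tells them to. For the BBB regression only the last row is available whichever reading is taken, because that model needs MRI.

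**Scans without contrast.** At an assumed 3–5% of the 30, 30 × 0.03 = 0.9 and 30 × 0.05 = 1.5, or about one subject. The imaging protocol includes the post-contrast FLAIR and the bolus T1 maps, so a scan without gadolinium has not completed it.

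**What an explicit contrast condition would cost.** The chance of reaching 30 within the cap is P(Bin(50, p) ≥ 30), where p is the product of the assumed retention rates:

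| MRI loss / no contrast | All 50 dosed: current rule | All 50 dosed: contrast rule | Further 10% lost before dosing: current rule | Further 10% lost before dosing: contrast rule |
|---|---|---|---|---|
| 20% / 3% | p=0.80: above 0.99 | p=0.776: above 0.99 | p=0.72: 0.98 | p=0.6984: 0.95 |
| 30% / 5% | p=0.70: 0.95 | p=0.665: 0.87 | p=0.63: 0.72 | p=0.5985: 0.55 |

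The current-rule columns count every scan, with or without contrast. Some loss before dosing is plausible, since every consented subject has an eye assessment before the first dose and a raised baseline QTc excludes.

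**The case for a change.** The strongest case for acting is that the three gaps are real and cheap to close. Nothing on the page forbids carrying the label into the cognitive analysis. The regression needs the 6-week score as well as the MRI, so an MRI-only count does not guarantee enough subjects for it. The list of drop-outs and the replacement sentence do not match. The study is meant to support a grant application, where clear denominators matter.

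All of this is true as description. What it does not show is that following the plan as written gives a wrong answer. The harm needs an analyst to add a restriction that is not there and to discard 6-week data the protocol takes care to collect. A case in numbers could be built from the precision lost, or the bias incurred, by restricting a mean change to MRI completers. It would rest on assumed rates and on one mean pooled over five dosing schedules, which the plan does not specify; the sign of any bias would be unknown. For the one model that is specified, widening the analysis set adds no subjects.

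The mismatch between the drop-out and replacement sentences also has an ordinary reading: the first explains the margin in enrolment, and the second says what fills a phase.

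**Conclusion.** No change is needed. MRI completion is the only written evaluability rule, and the 6-week endpoint itself does not need it. But the rule governs the filling of phases, where it fits the BBB readings, the scan-day samples, the regression on BBB disruption and the timing of escalation. It does not govern who enters the cognitive analysis.

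What remains is detail that a competent analyst would supply: the 6-week change in all dosed subjects with both scores, BBB outcomes in those with a contrast scan, and the regression in those with both. The contrast question concerns about one subject in 30 at assumed rates of 3–5%. Under a contrast rule, the chance of reaching 30 within 50 runs from 0.55 to above 0.99 depending on assumed losses, so a formal condition is not free either. The conclusion rests on the text not restricting the cognitive analysis and on 6-week follow-up being kept for subjects without MRI; it does not depend on any of the assumed rates.
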